The setting of Aim 1 will include not only the acute inpatient hospital (located on the West Roxbury Division Campus) but also the CLC, located on the Brockton Division Campus.

2. Recruitment and enrollment

Approximately ten (10) patients per week are discharged to home from the CLC each week. Because of the strong relationships developed between the clinical teams and the Veterans and their families during the long (compared with acute inpatient) hospitalizations, typically 3-4 weeks, Veterans are likely to be amenable to enrolling in a clinical research trial that they see their clinical team members advocating. Conservatively, we estimate that at least 2 patients each week will enroll in SMMRT, such that over the course of 12 months (50 weeks), a minimum of 100 patients would be enrolled. In addition, we have ensured that resources are available to enroll 140 patients at the West Roxbury setting, resulting in a total sample size of 240 subjects. Recruitment and enrollment processes will follow these steps:

1. Research staff will communicate regularly with clinical staff (nurses and clinicians) on the inpatient service at VA Boston's West Roxbury and Brockton Divisions
2. Research staff will identify any Veterans hospitalized on the Inpatient Service meeting the following criteria by reviewing CPRS, patient lists, and consulting with clinical staff:
 - a. age 18 years or older
 - b. having a VA primary care provider (PCP) at any VA facility in VISN-1
 - c. planned discharge home (as opposed to another facility)
 - d. anticipated to be discharged with at least 5 medications
3. Research staff will confirm with clinical staff that the Veteran/patient may be approached and informed about the study.
4. Research staff will approach the hospitalized Veteran to describe the study and seek informed consent for participation.
5. The research staff will briefly describe the study and then administer the Callahan cognition screener (see separate document) and the eligibility screening questions below.
6. If the Veteran passes the Callahan cognition screener and eligibility screening questions, the research staff member will seek to obtain informed consent and HIPAA Authorization.

Script for Aim 2 Eligibility Screening Questions (after Callahan Screening and before Informed Consent):

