We propose a two-arm RCT, with 120 participants in each arm. The main outcome measure will be combined number of medium- and high-significance medication discrepancies present at the 30-day follow-up. Conservative estimates suggest that we would expect a rate of 3.0 medium- or high-significance medication discrepancies per patient in the Usual Care group. Using a custom simulation, with two-tailed alpha error set at 5%, we calculated that this sample size (120 subjects per arm) would have 99.9% power to detect a lowering of the rate from 3.0 to 2.0 and 82% power to detect a lowering of the rate from 3.0 to 2.4.

6. Measures.

Study measures will be derived from baseline and 1-month follow-up interviews, as well as from CPRS.

Predictor Variable. The predictor variable will be the experimental condition (i.e., Usual Care SMMRT), assigned by random allocation (see above).

Main Outcome Variable. The primary outcome measure will be medication discrepancies detected 30 days after discharge. Secondary outcome measures will be 30-day hospital utilization (combined readmissions plus emergency department use) and Veterans' self-efficacy in medication use.

Secondary Outcome Variables. Secondary endpoints, ascertained through a combination of CPRS review

plus follow-up interview with participants, include community tenure (days spent outside of the hospital), medication discrepancies (overall and by subtype, i.e., omissions, commissions, duplications, and alterations in dose or frequency); health status (SF-12 health status scale; 12 items, 2-3 minutes), medication use self-efficacy (score of 0 to 8, based on validated 8-item yes/no MUSE scale;⁶² 3 minutes); and the Care Transition Measure (score of 0 to 100, based on validated 15-item, 4-point [strongly agree, agree, disagree, strongly disagree] scale, linear transformed to 0 to 100 scale,⁶³ 5 minutes).

Other Variables. Prior to randomization, we will stratify participants on the basis of My HealtheVet in-person authentication status (yes/no) and VA Boston primary care (yes/no); see above Figure 2 and Section 4.e.5. Baseline data will include age, educational level, race/ethnicity. At baseline, we will administer the 7-item REALM-SF health literacy scale,⁶⁴ the SF-12, and the medication use self-efficacy scale (MUSE). During the 30-day follow-up we will re-administer the SF-12, the CARE Transition measure and the MUSE.

7. Statistical Analysis.

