Preliminary Analyses. In preliminary analyses, descriptive statistics and bivariate associations will be computed. Then we will assess whether there are differences between the study arms for socio-demographic variables. We will assess imbalance formally using Analysis of Variance for continuous variables and Chi Square tests for dichotomous variables. In order to confound any observed effect of the treatment, a covariate must be imbalanced between the arms and also associated with the outcome. Thus, we will judge how plausible confounding is based on the formal tests, the degree of imbalance, and the plausibility of association with the outcome. Primary analysis will not include any potential confounders, but sensitivity analyses will adjust for plausible confounding variables with large imbalance between the arms.

Statistical Analyses. The primary hypothesis is that SMMRT will result in a reduction in 30-day medication discrepancies as compared with UC. The main outcome will be tested by a two-step analysis. First, we will conduct a logistic regression to compare SMMRT vs. UC. We will take an intent-to-treat approach to the analysis; Veterans will be included in our primary analyses regardless of their level of adherence with their assigned intervention. For participants who do not complete the telephone assessment, we will rely on CPRS/CDW data for outcome assessment.

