Checks and treatment for “non-Response” Bias. The potential for differential drop-out rates among the three groups is itself an interesting and important empirical question, with clinical implications. Drop outs will be defined as active drop outs (Veterans who request discontinuation of participation) and passive drop outs (Veterans who cannot be reached for follow-up within 60 days of discharge). Factors that may contribute to drop-out rate will be tested by logistic regression. This logistic regression will be used to generate completion probabilities, which we will use as Inverse Probability Weights (IPWs). We will then use the IPWs in a weighted logistic regression for the outcome as predicted by study arm. Heuristically, Veterans with low probabilities of response who do respond are upweighted to represent Veterans who did not respond. Veterans who were quite likely to respond will not be upweighted as much. The result is a weighted sample that resembles the original population. In the weighted analysis, we will use the robust or “sandwich” variance estimator to account for the variability added by estimating the IPWs.

Methods for Aim 2: In-Depth Interviews

Aim 2 . To evaluate MHV training and SMMRT interventions for potential future implementation. For this formative evaluation, we will use qualitative research methods to examine in-depth how Veterans perceived their interactions with the MHV Training and SMMRT intervention components. *We will also interview PACT RNs and Pharmacists to solicit their perspective on the integration of SMMRT into the post-discharge PACT workflow and will analyze related information collected from chart abstraction.*

Rationale for formative evaluation.

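### The stated 82% power belongs to a count comparison, but the only outcome models the plan names are logistic, with no outcome form or cut-off and no second step described

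*Combined protocol and SAP*

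**What the plan says.** All references are to the combined protocol and SAP, section (4), Methods for Aim 1.

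- **5. Sample size and power** makes the outcome a count: "The main outcome measure will be combined number of medium- and high-significance medication discrepancies present at the 30-day follow-up". With 120 per arm and a two-sided 5% level, it reports 99.9% power for a fall from 3.0 to 2.0 and "82% power to detect a lowering of the rate from 3.0 to 2.4". The figures come from a simulation whose distribution, dispersion, test and completion rate are not given.
- **7. Statistical Analysis, Statistical Analyses** says "The main outcome will be tested by a two-step analysis" and continues "First, we will conduct a logistic regression to compare SMMRT vs. UC". No cut-off or outcome form follows, and no second step is described. Patients who miss the telephone assessment are to have their outcome taken from CPRS/CDW records.
- **7. Statistical Analysis, non-response bias** defines active and passive drop-outs without an expected rate. It plans to "use the IPWs in a weighted logistic regression for the outcome as predicted by study arm".
- **2. Recruitment and enrollment** plans enrolment "resulting in a total sample size of 240 subjects", which is exactly 2 × 120.
- **4. Ascertainment of Outcome** obtains discrepancies by setting the patient's reported current medicines against the record.

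**The concern.** A power figure is useful only if it belongs to the test that will decide the trial. Here it describes a comparison of counts, while the analysis text names a model usually fitted to a binary outcome. Turning a count with mean 3 into yes/no discards information, and much of it when nearly every patient has at least one discrepancy.

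Two things are at stake. A null result would be read against 82% power that the written analysis may not have. And because the outcome form, the cut-off and the second step are all open, the primary analysis could be settled after the data are seen.

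**Working it through.** **Inputs from section 5:** n = 120 per arm; rates 3.0 vs 2.4 and 3.0 vs 2.0; two-sided 5%. **Assumptions of this check, because the documents give none:** Poisson counts, the cut-offs, the dispersion values and the loss rates.

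**Step 1. Reproduce the stated figure with a count test.** Wald test of the log rate ratio:
power = Φ(ln(λ₁/λ₂)/SE − 1.960), SE = √((1/λ₁ + 1/λ₂)/n).

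- 3.0 vs 2.4: SE = √(0.75/120) = 0.0791; ln(1.25) = 0.2231; ratio 2.823; power = Φ(0.863) = 80.6%. Simulation (40,000 runs; Poisson Wald, likelihood ratio, t-test) gives 80.5–80.9%. Stated: 82%.
- 3.0 vs 2.0: SE = √(0.8333/120) = 0.0833; ln(1.5) = 0.4055; ratio 4.866; power = Φ(2.906) = 99.8%. Stated: 99.9%.

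Both are reproduced to within 2 percentage points.

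**Step 2. The same counts analysed by binary logistic regression.** With treatment arm as the only term this is a two-proportion comparison. The proportions are Poisson tail probabilities, and power = Φ((p₁ − p₂ − 1.960·SE₀)/SE₁), with SE₀ pooled and SE₁ unpooled.

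| Cut-off | Rate 3.0 | Rate 2.4 | Power |
|---|---|---|---|
| ≥1 | 95.0% | 90.9% | 23.5% |
| ≥2 | 80.1% | 69.2% | 49.4% |
| ≥3 | 57.7% | 43.0% | 62.3% |
| ≥4 | 35.3% | 22.1% | 61.6% |
| ≥5 | 18.5% | 9.6% | 50.9% |

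Example at ≥3: difference 0.1465, SE₀ = 0.0645, SE₁ = 0.0639; (0.1465 − 1.960 × 0.0645)/0.0639 = 0.313; Φ = 62.3%. Simulated logistic likelihood-ratio tests agree: 25.0, 49.8, 60.6 and 62.5% for ≥1 to ≥4. Cut-offs of 6 and 7 give 35% and 21%. Reaching 82% at ≥3 would take 192 per arm. For 3.0 vs 2.0, any versus none has 62.9% and ≥3 has 98.0%.

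**Step 3. Ordinal logistic model.** The Wilcoxon test serves as a proxy for the proportional-odds test. Simulated power for 3.0 vs 2.4 is about 77–78%.

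**Step 4. Sensitivity of the count test (illustrative only).**

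- Variance/mean 1.5: multiplying the Step 1 SE by √1.5 gives 0.0968 and power Φ(2.305 − 1.960) = 63.5%. A negative binomial with common dispersion 0.5/3 has SE √((0.75 + 0.333)/120) = 0.0950 and power 65.1%. So about 64%.
- 10% full information loss: n = 108, SE = 0.0833, power Φ(2.678 − 1.960) = 76.4%.
- 10% non-completers kept through records, n still 120: about 81% if the records show the full arm difference, 76.7% if they show half of it, 71.6% if none.

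**The case against.** The strongest reply is that the plan's analysis is only half written, so its power cannot be declared deficient. Much of this stands.

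- **The second step may be a count model.** Nothing excludes it, and power would then return to about 81%. The weighted logistic model is a check for non-response bias, not evidently the primary test.
- **Logistic does not have to mean one dichotomy.** An ordinal model keeps most of the power. A discrepancies-per-medication logistic model could even exceed 82%: with 10 or 20 independent medications per patient (assumed figures) it gives about 91% or 86%. A reader might infer from Step 2 that a true fall to 2.4 would be missed at least 38% of the time. The documents do not support that as a general statement; it holds only for a single binary cut-off used as the primary test.
- **Loss may be small.** No rate is given. Reminders, rescheduling, a 60-day contact window and the record fallback all work against it. In the pilot (section (3)), record review alone identified 108 discrepancies in 51 Veterans, so records do carry information. They still lack the patient's side of the comparison that defines the outcome, so the fallback limits the loss argument without removing it.

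What does not fall away is that no count model appears anywhere in the plan, and the text does not say which test the 82% belongs to.

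**Conclusion.** The point holds as a mismatch between the power statement and the analysis text. A reader might infer that 82% is a calculation error; it is not, since a Poisson count comparison with all 120 per arm assessed gives about 81%.

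The size depends on what the unwritten parts mean: about 24% to at most 62% if the primary test is a binary logistic regression, about 77–78% if ordinal, about 81% if a count model is the deciding step. These figures rest on Poisson counts. Overdispersion and incomplete assessment lower the count-test power, by amounts the documents do not allow one to fix.

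It would also be tempting to say that 5% loss pushes the stated 82% below 80%. It does not: (1.960 + 0.915) × √0.95 − 1.960 = 0.842, which is 80.0%. Nor is 80% a target stated in the plan. The 3.0 vs 2.0 claim is not in dispute for a count test. The text should be changed; the design can stay.

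**What to change.** Keep 240 patients.

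- **7. Statistical Analysis, Statistical Analyses:** replace the logistic regression as the primary test with one test of the count that allows overdispersion, either negative binomial or Poisson with robust variance. A plain Poisson test would not do: its type I error, 2(1 − Φ(1.960/√(variance/mean))), is about 8%, 11% and 17% at variance/mean 1.25, 1.5 and 2. State what the second step is. If a dichotomy is intended, give its cut-off and its own power.
- **7. Statistical Analysis, non-response bias:** use the same count model in the weighted analysis.
- **5. Sample size and power:** say which test the power belongs to, and restate it over a stated dispersion range (the pilot's variance if available, otherwise for example variance/mean 1 to 2) and interview completion range (for example 80–100%).

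The cost is one re-run of the simulation and a few reworded sentences. The downside is that the stated power for 2.4 becomes somewhat less favourable.

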the approach developed by Lesselroth et al,³ we will use automated processes to populate the SMMRT with the medication list and MIL images. After reviewing the SMMRT, the Pharmacist sends it via SM to the Veteran, who receives the SM, downloads the SMMRT, and reviews it for accuracy (in comparison with home medications). We learned from our pilot study that only about half of Veterans had their medications present when completing the SMMRT; our training for the proposed trial will include encouragement to have medications present while completing the SMMRT. Following review and correction, the Veteran returns the SMMRT to the Pharmacist within 3 business days, initiating a possible back-and-forth exchange of messages (or telephone calls) to confirm medication accuracy; this exchange is represented in the middle of the figure with bidirectional arrows. The pharmacist confers with PCP for clinically urgent or uncertain issues (occurred in only two cases during the pilot study) and documents medication reconciliation in CPRS. Finally, the pharmacist sends the final revised SMMRT to the Veteran. The research associate monitors the initiation of the exchange and will prompt either the pharmacist or the veteran to respond within 3 business days, via phone. The veteran will be informed at the beginning of the study and at the end if appropriate that access to the pharmacist ends in 30 days.

4. Ascertainment of Outcome

Outcomes will be ascertained via 30-day telephone interview (see Telephone Script for 30-Day Follow-up Call) and chart review. The research associate will send out a written reminder a few days before the 30 day follow-up call, and make a reminder call the day before the interview, to remind the veteran to have their medications ready. The research associate will ascertain the medications that the subject is currently taking, and the research associate will then compare that list with the medication list in the medical record to identify discrepancies. We will distinguish medication discrepancies as being of a) high significance, b) moderate significance, or c) low significance, based on how likely they would be to result in patient harm.

In the event the veteran was not reached for the interview, the research associate will send out a letter and call the veteran to reschedule the interview.

5. Sample size and power

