management software tool.⁷¹ Team members will meet regularly to review the coding strategies and themes that emerge from further analysis of the thematic and categorical reports that will be generated following coding. We will continue analysis until no new major themes emerge. We will address recognized criteria for qualitative research: credibility, fittingness, auditability, and confirmability.⁷²

(5) HUMAN SUBJECTS

The overall goal of this project is to evaluate the Secure Messaging for Medication Reconciliation Tool (SMMRT) for the purposes of post-discharge medication reconciliation. This project proposes two types of research: Aim 1 is quantitative: an RCT to compare the effect of an intervention on the medication reconciliation process following discharge from the hospital. Aim 2 is qualitative, gathering the preferences, attitudes, and behaviors of Veterans and VA pharmacists and nurses regarding the SMMRT tool and its implementation.

Aim 1: Risk to Subjects

Human Subjects Involvement and Characteristics

The goal of Aim 1 is to conduct a two-arm RCT to evaluate the effects of SMMRT. This trial will compare 1) Usual Care (UC) with 2) UC plus pharmacist-mediated medication reconciliation via SM using SMMRT among Veterans discharged from the hospital. A total of 240 Veterans will be recruited for Aim 1 once deemed appropriate for the study. The study will be explained to Veterans who express interest, and informed consent will be obtained. Veterans will be informed that their care will not be affected if they choose not to participate in the study. Next, Veterans will be randomized to condition, and the baseline interview will be administered. If the Veteran is randomized to UC plus SMMRT, the research associate will instruct the Veteran on how the tool works. When the Veteran has completed the training with the SMMRT tool, the research associate will ensure no other questions remain. Veterans in the UC plus SMMRT Intervention condition will be monitored during the length of the study. A total of 20 Veterans from the experimental arm of Aim 1 will be contacted for a post- intervention in-depth interview (See Aim 2 below).

Sources of Materials

Data to assess the outcomes of the RCT will be derived from review of the medical record (CPRS and VistAWeb), the *Corporate Data Warehouse (CDW)*, and telephone-based interviews with participants.

Potential Risks

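### The data source for 30-day hospital utilization and community tenure depends on whether the Veteran completes the follow-up call; one record source should be used for all 240

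*Combined protocol and SAP*

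**What the plan says.** Four places in the combined protocol and SAP bear on the source of these outcomes.

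- **Methods for Aim 1, 4. Ascertainment of Outcome.** The general rule is "Outcomes will be ascertained via 30-day telephone interview (see Telephone Script for 30-Day Follow-up Call) and chart review".
- **6. Measures.** The opening line says "Study measures will be derived from baseline and 1-month follow-up interviews, as well as from CPRS". Hospital utilization is then named: "Secondary outcome measures will be 30-day hospital utilization (combined readmissions plus emergency department use". The next paragraph begins "Secondary endpoints, ascertained through a combination of CPRS review" and continues "plus follow-up interview with participants, include community tenure". Community tenure (days outside the hospital) is thus explicitly a records-plus-interview outcome. Utilization is not repeated in that list.
- **7. Statistical Analysis, Statistical Analyses.** The rule for missed calls is "For participants who do not complete the telephone assessment, we will rely on CPRS/CDW data for outcome assessment".
- **(5) Human Subjects, Aim 1, Sources of Materials.** Here the plan says "Data to assess the outcomes of the RCT will be derived from review of the medical record (CPRS and VistAWeb", then adds the Corporate Data Warehouse "and telephone-based interviews with participants".

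The paragraph on non-response bias in section 7 foresees that drop-out may differ between groups. It plans a logistic regression weighted by inverse completion probabilities. It does not say whether the weighting covers utilization or community tenure, or how it fits with the CPRS/CDW fallback. No analysis of utilization is described anywhere.

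**The concern.** An outcome should be measured with the same completeness in everyone, or at least with a completeness unrelated to arm. Here completeness follows call completion, and call completion happens after randomization. Only the SMMRT arm has a pharmacist exchange and telephone prompts during follow-up, so unequal completion is plausible; the plan itself raises the possibility.

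Any event that the interview would reveal but the records do not is counted for a completer and lost for a non-completer. Non-VA admissions and emergency visits are the obvious candidates, because every record source named is a VA system. The arm with more missed calls would then look better: fewer Veterans with hospital use, and more days in the community. A larger sample would not remove the error. Reducing hospital utilization is part of the trial's stated rationale, so a reader will give this comparison weight.

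**Working it through.** **The plan's own figures.** The plan gives none for utilization. Its power figures concern the primary discrepancy count with 120 per arm. A two-sided Poisson comparison gives 99.8% for 3.0 to 2.0 (stated 99.9%) and 80.6% to 80.9% for 3.0 to 2.4 (stated 82%). They reproduce closely and do not bear on this point.

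**Inputs.**

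- *p*, the proportion with any 30-day use. The background section on medication discrepancies and hospital utilization gives 14–20% readmitted and more than 30% seeking emergency care. I take 30% to 40%.
- *s*, the share of users whose only use was outside VA and is absent from the records. The documents do not give it. Assumed 10% to 40%.
- *d*, the proportion missing the call in each arm. The documents do not give it. Assumed 15% vs 25%, or 10% vs 30%.
- *n* = 120 per arm (5. Sample size and power).
- Benchmark: a 23% relative reduction in readmissions and emergency visits, from the systematic review described under Medication Reconciliation: Policies and Approaches.

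**Formula.** Suppose there is no true effect, *s* is the same in both arms, and missing the call is unrelated to hospital use. The observed rate in an arm is then *p*(1 − *s·d*), and

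false difference = *p* × *s* × (difference in *d*).

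**Results.** The last column is the two-sided rejection probability with no true effect, by normal approximation with unpooled variance; the nominal value is 5%.

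| *p* | *s* | missed calls | false difference | rejection probability |
|---|---|---|---|---|
| 30% | 10% | 15% vs 25% | 0.30 × 0.10 × 0.10 = 0.3 points | 5.0% |
| 35% | 25% | 15% vs 25% | 0.35 × 0.25 × 0.10 = 0.9 points | 5.2% |
| 30% | 25% | 10% vs 30% | 0.30 × 0.25 × 0.20 = 1.5 points | 5.8% |
| 40% | 25% | 10% vs 30% | 0.40 × 0.25 × 0.20 = 2.0 points | 6.2% |
| 35% | 40% | 10% vs 30% | 0.35 × 0.40 × 0.20 = 2.8 points | 7.5% |

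If *s* = 0, or if the arms miss calls equally often, the false difference is 0.

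**Scale.** The standard error of the difference at 35% use is √(2 × 0.35 × 0.65 / 120) = 6.2 points. The benchmark effect at 35% is 0.35 × 0.23 = 8.1 points, so the top row of the range is 2.8 / 8.1, about a third of it. Power for a real 23% reduction is only 23% (at 30% use) to 32% (at 40% use).

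**One source for everyone.** Read from records alone, each arm shows *p*(1 − *s*). With equal *p* and *s* the false difference is 0 at any gap in missed calls.

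**Community tenure.** The same mechanism applies in days: mean uncharted non-VA hospital days × gap in missed calls, in the direction of falsely high tenure. The documents give nothing from which to size it.

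**The case against.** The other side has several fair points.

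- **The link to utilization is indirect.** The fallback sits in a paragraph about the main outcome, and utilization is missing from the list of outcomes taken from records plus interview. This stands in part. The fallback's wording is general, as is the ascertainment rule, and community tenure is listed expressly.
- **The premise cannot be checked.** The documents do not say what CPRS, VistAWeb and CDW show of outside care. Every participant has a VA primary care provider, so outside events may reach the chart. The telephone script is a separate document; if the call does not ask about hospital use, utilization has no mixed source. This stands, and it is why the size is conditional.
- **Mitigation exists.** The plan provides reminders, rescheduling and the inverse-probability weighting. Weighting limited to completers would avoid mixed sources, but the plan neither applies it to these outcomes nor reconciles it with the fallback.
- **A records-only count has its own weakness.** If SMMRT moves care toward VA sites, *s* differs by arm and the count is biased even with complete follow-up. At 35% use, a difference of 8 points in *s* gives 0.35 × 0.08 = 2.8 points. This stands, and the completer analysis is needed beside it for that reason.

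A reader might also infer that pharmacist documentation raises capture of non-VA events in the SMMRT arm. The documents do not support this: they say the pharmacist records medication reconciliation, not hospital use.

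**Conclusion.** The point holds in a limited form. Call completion decides which sources feed community tenure (explicitly) and 30-day utilization (by the general wording), and nothing in the plan reconciles this. To the extent that the records miss non-VA use, utilization reads falsely low in the arm with more missed calls, by about 0.3 to 2.8 points under the assumed inputs. That is less than half of the 6.2-point standard error, so imprecision is the larger problem for this outcome.

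Two stronger readings are tempting and should be resisted. One is that a missed call is coded as no non-VA use; the documents never mention non-VA use and state no such coding. The other is that any drop-out difference becomes a false arm difference. Only the fraction *p* × *s* of the gap passes through, and nothing does if the records are complete.

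The use rate, the non-VA share and the missed-call rates are all assumptions. So is independence between missing the call and hospital use; if Veterans with outside admissions are harder to reach, the error could exceed the formula.

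**What to change.** In 6. Measures and 7. Statistical Analysis:

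1. For the main between-arm comparison of 30-day utilization and community tenure, use the same record sources (CPRS, VistAWeb and CDW) for all 240 Veterans, whether or not they completed the call.
2. Beside it, report the records-plus-interview version among completers only, with the inverse-probability weights from the non-response paragraph. State that the weighting covers these two outcomes.
3. State that a missed interview is not treated as absence of non-VA use.

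The cost is wording, since all the sources are already listed. The downside is that the headline figure leaves out non-VA events the records do not show, and assumes that the share of care sought outside VA is similar in both arms. The weighted completer analysis is the check on that assumption. It has fewer Veterans and depends on the drop-out model, so it should support the records-based comparison, not replace it.
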